13. SPECIMEN BANKING

- *If specimens will be banked for future research, describe where the specimens will be stored, how long they will be stored, how they will be accessed and who will have access to the specimens*
- *List the information that will be stored with each specimen, including how specimens are labeled/coded*
- *Describe the procedures to release the specimens, including: the process to request release, approvals required for release, who can obtain the specimens, and the information to be provided with the specimens.*

--

14. DATA MANAGEMENT AND CONFIDENTIALITY

- *Describe the data and specimens to be sent out or received. As applicable, describe:*
 - *What information will be included in that data or associated with the specimens?*
 - *Where and how data and specimens will be stored?*
 - *How long the data will be stored?*
 - *Who will have access to the data?*
 - *Who is responsible for receipt or transmission of data and specimens?*
- *Describe the steps that will be taken to secure the data during storage, use and transmission.*

--

15. DATA AND SAFETY MONITORING PLAN

A specific data and safety monitoring plan is only required for greater than minimal risk research. For guidance on creating this plan, please see the [Guidance Document](#) on the HRPP website.

- *Part I – this part should be completed for all studies that require a DSMP.*
- *Part II – This part should be completed when your study needs a Data and Safety Monitoring Board or Committee (DSMB/C) as part of your Data and Safety Monitoring Plan.*

Part I: Elements of the Data and Safety Monitoring Plan

- *Indicate who will perform the data and safety monitoring for this study.*
- *Justify your choice of monitor, in terms of assessed risk to the research subject's health and well being. In studies where the monitor is independent of the study staff, indicate the individual's credentials, relationship to the PI, and rationale for selection*
- *List the specific items that will be monitored for safety (e.g. adverse events, protocol compliance, etc)*
- *Indicate the frequency at which accumulated safety and data information (items listed in # above) will be reviewed by the monitor (s) or the DSMB/C.*

- *Where applicable, describe rules which will guide interruption or alteration of the study design.*
- *Where applicable, indicate dose selection procedures that will be used to minimize toxicity.*
- *Should a temporary or permanent suspension of your study occur, in addition to the IRB, indicate to whom will you report the occurrence.*

The research material collected will be data from focus groups, self-reported internet surveys, self-report assessment questionnaires, and medical record abstraction data. The questionnaire and qualitative interview data will be collected specifically for the proposed research project. The medical chart data is collected in the regular course of patient treatment. All data pertaining to individual subjects will be identified only by code number and kept in a locked file cabinet at [name]. Only the study personnel will have access to links between subjects and subject identities. Upon completion of a subject's participation, these links will be destroyed. De-identified questionnaire data will be entered into an electronic database (REDCap) stored in a password-protected and encrypted secure folder. Digital audio recordings of advisory board meetings and usability testing will be transcribed without identifiers. The researchers take the issue of confidentiality very seriously. Extensive efforts will be undertaken to maintain study participants' confidentiality and privacy. Upon study entry, each study subject will be given a unique numeric identifier. All study materials (focus groups voice files, focus group transcriptions, self-reported internet surveys, self-report assessment questionnaires, and medical record abstraction data, and any subsequent databases generated for the study) will be stored in locked file cabinets to which only study staff will have access. Informed consent forms will be filed in separate locked file cabinets. Identifying information, such as a patient's name, will not be included in the data files, such as the completed questionnaires or any study databases.

In addition, The Principle Investigators will meet with the RC's on a regular basis to ensure data accuracy and protocol adherence. Quarterly meetings (either in person or via phone) with the entire study team will also ensure protocol adherence. To ensure the validity and integrity of study data, the PIs will also oversee all data management responsibilities. The PIs will discuss all data management issues with the study team at NWH and FCCC/Temple.

The Feinstein Institute for Medical Research will be used as a central location for data processing and management. Vanderbilt University, with collaboration from a consortium of institutional partners, has developed a software toolset and workflow methodology for electronic collection and management of research and clinical trial data. REDCap (Research Electronic Data Capture) data collection projects rely on a thorough study-specific data dictionary defined in an iterative self-documenting process by all members of the research team with planning assistance from the Biostatistics Unit of the *Feinstein Institute for Medical Research*. The iterative development and testing process results in a well-planned data collection strategy for individual studies. REDCap servers are housed in a local data center at the

Feinstein and all web-based information transmission is encrypted. REDCap was developed specifically around HIPAA-Security guidelines and is recommended to Northwell Health researchers by both our Clinical Research Service, Research Compliance Office and Institutional Review Board. REDCap has been disseminated for use locally at other institutions and currently supports 965 active institutional partners and other institutions in 78 countries (www.project-redcap.org).

Part II: Data and Safety Monitoring Board or Committee

- *When appropriate, attach a description of the DSMB.*
- *Provide the number of members and area of professional expertise.*
- *Provide confirmation that the members of the board are all independent of the study.*

--

16. WITHDRAWAL OF SUBJECTS

- *Describe anticipated circumstances under which subjects will be withdrawn from the research without their consent*
- *Describe procedures for orderly termination*
- *Describe procedures that will be followed when subjects withdraw from the research, including partial withdrawal from procedures with continued data collection.*

Circumstances in which participants may be withdrawn from the research without their consent may include the following:

- Failure to follow instructions,
- Failure to adhere to scheduled study visits,
- If it is not in your best interest to continue on this study, or
- If the study is stopped

This decision may be made by the PIs, or the IRB.

Participants will be able to withdraw from the study at any time. The consent form will make explicit to patients that they may discontinue the study at any time without penalty and without prejudice to their medical care.

Any subjects withdrawn from the research, including partial withdrawal from RCT phase where continued data collection will occur will be instructed that per the consent form we may still use information we have already collected for research purposes but will not continue to collect any further data. Finally, the subject will have their information removed from any future correspondence that was planned for the study.

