Specific Aim 2: Conduct a rigorous 12-month randomized controlled trial with BC patients and their caregivers at three diverse hospital systems. Patient and caregivers (N=287 participants) will be randomized into the (a) RSBC intervention or (b) time and attention comparison condition that incorporates appropriate health promotion adapted from our prior work (final N= 238 participants). Patients and caregivers in the intervention group compared to the comparison group will experience improved QOL (**primary outcome**) both in the short- (6 mo post-op) and long-term (12 mo post-op; H1), and will experience fewer infections and nurse/ER visits (patients only, **secondary outcomes**; H2).

Specific Aim 3: Conduct moderator and mediator analyses. 3a: To examine the impact of identified moderators on intervention efficacy. Older age, female gender, and type of surgical diversion (i.e., non-neobladder) will moderate the relationship between the intervention and QOL (H3). **3b:** To examine the impact of identified

mediators on intervention efficacy. Higher levels of patient activation (i.e., self-care knowledge, self-efficacy) and lower levels of distress will mediate the intervention effect (H4).

Exploratory Aim 4: To examine the costs and potential savings associated with developing and implementing the RSBC intervention. Costs will be recorded in three categories: development, implementation, and maintenance of intervention. Potential savings will be recorded regarding emergency room care and unplanned visiting nurse home visits. Over time, the savings from the reduced ER/Nurse visits will surpass the costs of the intervention (H5) and the intervention will be cost effective (H6).

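### Section 16 allows withdrawal for non-adherence and then ends data collection, permitting avoidable loss of later outcomes, and it contradicts itself on partial withdrawal

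*Combined protocol and SAP*

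**What the plan says.** Section 16 (Withdrawal of Subjects) opens its list with "Circumstances in which participants may be withdrawn from the research without their consent may include the following". Two of the four entries concern adherence: "Failure to follow instructions" and "Failure to adhere to scheduled study visits". On authority it says "This decision may be made by the PIs, or the IRB".

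On data after withdrawal, the section covers any withdrawn participant and says "we may still use information we have already collected for research purposes but will not continue to collect any further data". It adds that the participant is taken off planned study correspondence. The same sentence includes, among those it covers, cases of "partial withdrawal from RCT phase where continued data collection will occur".

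Other sections bear on this:

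- Section 4 places the primary QOL hypothesis at 6 and 12 months post-op and names infections and nurse/ER visits (patients only) as secondary outcomes.
- Section 6 lists assessments at baseline and 1, 3, 6 and 12 months.
- Section 11 allows every follow-up assessment to be done by REDCap link, mail, phone or in person. It gives the RSBC arm a website login (and a tablet if no device is available) and the control arm brochures.
- Section 12 specifies a linear mixed effect model for QOL. It names no as-randomised analysis set, missing-data method or sensitivity analysis.
- Section 15 lists medical record abstraction as a data source and says chart data arise in routine care.

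**The concern.** Both adherence reasons arise after randomisation and may be related to outcome. If they end outcome collection, participants leave follow-up because of how they behaved after allocation. Someone withdrawn over a missed 1- or 3-month assessment loses both primary time points, so a gap that a mixed model could tolerate becomes permanent dropout. Record-based information stops as well, although it needs no study visit.

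The loss could also differ by arm. The two arms have different materials to use, website use is logged for one of them (Section 12), and no masking of those who decide on withdrawal is described. The randomised comparison would then be partly a comparison of people who complied.

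Separately, the sentence on data after withdrawal cannot be followed as written. Site staff cannot tell whether a partly withdrawn participant should still be followed.

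**Working it through.** **Step 1. The two clauses.** One clause describes partial withdrawal with data collection continuing. The operative clause says collection ends for any withdrawn participant, partial cases included. Both cannot hold. The section defines no status in which a participant stops the study materials but stays in follow-up.

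**Step 2. How much loss is planned.** Sections 5 and 8 give 287 enrolled, 238 final and 15% attrition.

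- 287 × 0.85 = 244, against 238 stated. Conversely, 238 / 0.85 = 280, against 287 stated. Both agree within 3%.
- Exact implied loss: (287 − 238) / 287 = 49 / 287 = 17.1%.
- Section 5 also gives 70% retention in the same sentence: 287 × 0.70 = 201, a loss of 86. This does not reproduce 238.

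The documents do not say how many losses would be investigator withdrawals. The number of participants whose later outcomes the fix could preserve is therefore anywhere from 0 to 49, or 0 to 86 under 70% retention.

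**Step 3. Possible bias (illustration).** Let L be the share lost in an arm and g the retained-minus-lost difference in mean QOL, in SD. The mean among those retained exceeds the full-arm mean by L × g, so a simple contrast of retained participants shifts by

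L(RSBC) × g(RSBC) − L(control) × g(control).

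Neither L by arm nor g is in the documents. The assumed g is 0.25 to 0.5 SD.

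- Equal loss and equal gap: 0.
- Loss 20% v 10%, same gap: 0.10 × 0.25 = 0.025 to 0.10 × 0.5 = 0.05 SD.
- Loss 30% v 15%, same gap: 0.15 × 0.25 = 0.0375 to 0.15 × 0.5 = 0.075 SD.

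The sign reverses if the control arm loses more.

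**Step 4. Effect on the error rate.** Assume 1:1 allocation, a two-sided 5% test and a normal approximation. The standard error in SD units is √(4/n): √(4/153) = 0.162 for patients and √(4/85) = 0.217 for caregivers (final numbers from Section 8).

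- Bias 0.025 SD: the 5% error becomes 5.3% (patients) and 5.2% (caregivers).
- Bias 0.075 SD: 7.5% and 6.4%.

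These figures are for a simple comparison of retained participants. The planned mixed model uses QOL recorded before withdrawal and removes the part of the bias which that QOL explains.

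**The case against.** The strongest reply is that the section only permits withdrawal. It sets no threshold or expected frequency, and the decision is discretionary. Data already collected are kept and enter the mixed model. The partial-withdrawal clause suggests that continued follow-up was intended in some cases. With remote completion available, a sick participant need not attend a clinic. All of this stands, and it limits the point to what the rule allows.

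A reader might go further and infer that outcomes will be lost selectively by arm, mainly among RSBC participants, and in RSBC's favour. The documents do not support that. Section 11 sets no minimum website use, and Section 12 plans to correlate usage with outcomes, so varying use is expected. Nothing names low use as a reason for withdrawal. The assessment schedule is not said to differ by arm. If missed assessments track illness and RSBC helps, the control arm could lose more sick participants and the bias would run against RSBC.

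A reader might also assume that infections and ER visits are mainly taken from charts. Section 15 lists record abstraction as a source but does not tie it to particular outcomes.

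**Conclusion.** The wording defect is certain. Section 16 contradicts itself on continued collection, and its operative clause lets non-adherence or a missed visit end outcome follow-up. Nothing in Section 12 offsets this. The consequence is a permitted, avoidable loss of 6- and 12-month QOL and of later infection and nurse/ER data. That loss would be adherence-related and possibly arm-related.

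The resulting bias is not established in size or direction. The illustrative 0.025 to 0.075 SD rests on assumed differences in loss and assumed QOL gaps, may take either sign, and comes before the mixed model's correction. It is tempting to express it as a share of the effect the trial could detect, but the plan states no effect size, SD or power. The point should be fixed, but it ranks below a defect that must be fixed before the trial can be relied on. High confidence applies to the wording only.

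**What to change.** Amend Section 16 and the matching consent wording:

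1. Reconcile the sentence on data after withdrawal so that it says one thing about partial withdrawal.
2. Remove failure to follow instructions and missed visits as grounds for ending outcome follow-up. The other two listed grounds are not affected.
3. Define two separate statuses: (a) stopping use of the study materials or missing an assessment, after which questionnaires (REDCap, mail or phone) and medical record abstraction continue to 12 months; and (b) withdrawal of consent for data collection, where the participant is asked whether record abstraction may continue.
4. State in Section 12 that all randomised participants are analysed in their assigned arm.

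The cost is an IRB amendment with revised consent text and some extra follow-up contact. The follow-up modes needed are already in Section 11. The documents contain no budget, so whether the extra contact is funded should be checked.

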17. RISKS TO SUBJECTS

- *Describe any potential risks and discomforts to the subject (physical, psychological, social, legal, or other) and assess their likelihood and seriousness and whether side effects are reversible. Where appropriate, describe alternative treatments and procedures that might be advantageous to the subjects.*
- *Include risks to others , like sexual partners (if appropriate)*
- *Discuss why the risks to subjects are reasonable in relation to the anticipated benefits and in relation to the importance of the knowledge that may reasonably be expected to result.*
- *Describe the procedures for protecting against or minimizing any potential risks, including risks to confidentiality, and assess their likely effectiveness.*

[There is a slight risk that participants might be distressed or uncomfortable when being asked questions about their BC. All research personnel with patient contact will be trained by [name], to be vigilant and sensitive to expressions of distress. All participants will be encouraged to contact the PI if any concerns arise. In the event of high levels of distress, the patient will be referred to counselors in the Department of Social Work, or appropriate medical health professionals.

The risks to subjects are reasonable in that this is a minimally invasive study, no subject's treatment will be altered in any way and the only potential risk is that of distress with questions being asked which they are free to skip. The risks are outweighed by the anticipated benefits and knowledge to be gained that may help men and women in the future in addition to providing subjects with enhanced knowledge and awareness of bladder cancer.

The procedures to protect subjects against or minimize the described risks in addition to risks to confidentiality include allowing participants to skip or choose not to respond to any questions that may cause them distress. Confidentiality will be protected by ensuring that all patient information gathered will be kept on Northwell's secured server and in password protected files that only the research team has access to. Further, information will only be accessed when needed and the research team will be trained to ensure confidentiality and the correct procedures when accessing and saving patient information are used.

18. RESEARCH RELATED HARM/INJURY

- *Describe the availability of medical or psychological resources that subjects might need as a result of anticipated problems that may be known to be associated with the research.*
- *If the research is greater than minimal risk, explain any medical treatments that are available if research-related injury occurs, who will provide it, what will be provided, and who will pay for it.*

[We do not anticipate any risks to participants beyond the potential discomfort of thinking about and discussing, bladder cancer patients' informational support and

health care needs. Loss of confidentiality may occur if someone other than those on the study team were to access the audio recording. However, measures will be taken to ensure that only the investigators listed on this IRB application will have access to the study data including the audio recordings.

Patients may be at risk for slight emotional distress, which might result from being asked questions about personal cancer and treatment experiences. Participants will be informed during the focus group sessions and at the beginning of the assessment that potentially sensitive topics will be discussed and that they may skip any part that would make them uncomfortable. Further, all study personnel involved in the study will be trained by the PIs to recognize distress and embarrassment of participants and will be instructed to address any distress caused by the study in a sensitive and supportive manner. Although unlikely, any patient requesting consultation will be referred immediately to the Principle Investigator.

19. POTENTIAL BENEFIT TO SUBJECTS

- *Explain what benefits might be derived from participation in the study, noting in particular the benefit over standard treatment (e.g. a once-a-day administration instead of four times a day, an oral formulation over an IV administration).*
- *Also state if there are no known benefits to subjects, but detail the value of knowledge to be gained*

Empirical data from the advisory board meetings will be used to develop an innovative multimodal intervention to help patients and caregivers cope with BC and to facilitate adjustment being a survivor of bladder cancer after treatment. Data from the longitudinal surveys will ultimately be used to inform the future development of information and emotion-focused interventions that will improve well-being and help patients with BC better cope with life after cystectomy and urinary diversion. The proposed study is also aimed to examine the costs and benefits of the RSBC intervention to facilitate integration into clinical practice.

20. PROVISIONS TO PROTECT PRIVACY INTERESTS OF SUBJECTS

- *Describe the methods used to identify potential research subjects, obtain consent and gather information about subjects to ensure that their privacy is not invaded.*
- *In addition consider privacy protections that may be needed due to communications with subjects (such as phone messages or mail).*

Patients diagnosed with BC will first be identified by the participating physicians at each study site (NWH, FCCC/TUH). A registry of these potential BC patients will be developed and reviewed on a monthly basis by a physician at each practice site. The physician will review the medical record and determine whether these patients

are diagnosed with biopsy confirmed BC. Eligible patients will be called by the CRC/RA prior to enrollment to assess interest. If the patient and their caregiver are willing to participate, the CRC/RA will schedule a time to review the study, aiming for 1 week prior to surgery (or at an alternate time that is convenient for the participant) for enrollment, baseline, and pre-treatment intervention. On the day of their visit, the CRC/RA will approach the patient and their caregiver. If patient and caregiver agree to participate, they will be asked to sign IRB approved consent forms once the study has been fully explained to them and after they have had an opportunity to ask clarifying questions. The researchers take the issue of confidentiality very seriously. Extensive efforts will be undertaken to maintain study participants' confidentiality and privacy. For HIPPA privacy purposes, participants will be informed that their names are not attached to study documents. In addition, ongoing protection of confidentiality will be adhered to throughout the study period and thereafter and to ensure the utmost validity and integrity of study data, the PIs will also oversee all data management responsibilities and will discuss all data management issues with the study teams at each site. Any phone calls or emails will be sent to participants through the respective study site's secured server and calls made at each study location in a secured area.

